**Table 1 Schedule of Activities (SoA)**

|              | Screening                   |               | Treatment Period |             |                |             |                |             |                | EDV | Safety Follow-up period   | Final Follow-up Visit | Details in CSP Section or Appendix |
|--------------|-----------------------------|---------------|------------------|-------------|----------------|-------------|----------------|-------------|----------------|-----|---|-----------------------|------------------------------------|
|              | 1                           | 2             | 3                | 4           | 5 a | 6           | 7 a | 8           | 9 a |     |   |                       |                                    |
| Visit Number |                             |               |                  |             |                |             |                |             |                |     | 10, 11 a ,
12, 13 a ,
14, 15 a | 16                    |                                    |
| Study Week   |                             |               | 0                | 1           | 3              | 4           | 6              | 8           | 10             |     | 12, 14,
16, 18,
20, 22  | 24                    |                                    |
| Study Day    | D-42 to
D-1  | D-7 to
D-1 | D1               | D8          | D22            | D29         | D43            | D57         | D71            |     | D85,
D99,
D113,
D127,
D141,
D155                       | D169                  |                                    |
| Visit Window |                             |               |                  | ± 1
days | ± 2
days    | ± 2
days | ± 2
days    | ± 2
days | ± 2
days    |     | ± 2
days   | ± 2
days           |                                    |

Note: Participants are required to fast for at least 8 hours overnight prior to all study visits except for Visit 1; Participants are permitted to drink water during this period of fasting until 1 hour before blood sampling. On days where participants attend the clinic in a fasted state, blood and urine samples should be obtained prior to administration of IP.

Note: Samples to be obtained from all treatment arms unless specified in the table.

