- a Home visits: may be undertaken at the participant’s home or any other appropriate location by site staff or by qualified external service provider. Other visits currently not designated as ‘home visits’ may also be undertaken at the participant’s home or any other appropriate location if deemed applicable, following consultation with the Investigator and the sponsor. Home visits performed by qualified external service provider (i.e. not by clinical trial site personnel) may only be performed starting Visit 5 (D22), excluding dosing visits (Visit 6 (D29) and Visit 8 (D57)).
- b Check screening labs and inclusion/exclusion criteria.
- c Weight should be measured in light indoor clothes, without shoes, after a prior visit to the bathroom.
- d Injection Site Reaction assessments to be collected based on adverse event collection criteria.
- e Vital signs and ECG to be measured pre-dose on dosing days.
- f ECG to be performed during the safety follow up period at Visits 10 (D85), 11 (D99), 13 (D127), and 15 (D155).
- g Blood samples for complement activation panel and coagulation parameters will be taken around Cmax and are to be collected pre-dose and 2 hours post-dose.
- h Samples to be obtained pre-dose on dosing days.

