##### **Type of Participant and Disease Characteristics**

- 2 Participants who have a fasting LDL-C  $\geq 70$  mg/dL (1.8 mmol/L) but  $< 190$  mg/dL (4.9 mmol/L) at screening (Visit 2).
- 3 Have fasting triglycerides  $< 400$  mg/dL ( $< 4.52$  mmol/L) at screening (Visit 2).
- 4 Should be receiving moderate- or high-intensity statin therapy (refer to [Appendix H](#)) as defined by the ACC/AHA guidelines on blood cholesterol management, or according to local guidelines.
- 5 Should be on stable medication for  $\geq 3$  months prior to screening with no planned medication or dose change during study participation. The exception to this restriction is for fenofibrate; if the participant is receiving fenofibrate, the therapy must be stable for at least 6 weeks prior to randomization at a dose that is appropriate for the duration of the study in the judgement of the Investigator. Other fibrate therapy (and derivatives) are prohibited.

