### General description of visits:

**Visit 1 (enrolment) and Visit 2:** At Visit 1 (Day -42 to Day -1), participants will be asked to

sign the informed consent and optional informed consent for future genetic research sample. Participant demographics, medical history including smoking and alcohol consumption history will be recorded in the eCRF. A complete physical examination must be performed. Vital signs, height, BMI and ECG must be checked, as well as blood and urine sample collection. Enrolment will be performed in RTSM. Visit 2 (Day -7 to Day -1) will include an blood sample collection for LDL-C, PCSK9, and triglycerides.

**Visit 3 (randomization):** Visit 3 (Day 1) should be performed within 42 days of Visit 1. Participants are required to fast for at least 8 hours overnight, prior to the visit; participants are permitted to drink water during this period until 1 hour before blood sampling. At Visit 3, eligibility criteria must be verified by checking screening labs and inclusion/exclusion criteria. A complete physical examination must be performed. Blood and urine samples to be obtained prior to administration of study intervention in fasted state. ADA sample will be obtained pre-dose. Vital signs and ECG to be checked. If the participant fulfils all inclusion criteria and none of the exclusion criteria, they will be randomized in RTSM and study intervention will be administered as SC injection.

**Visit 4, 6, and 8:** Visit 4 (Day 8  $\pm$  1 day), Visit 6 (Day 29  $\pm$  2 days), and Visit 8 (Day 57  $\pm$  2 days) are planned as clinical visits but may also be undertaken at the participant's home or any other appropriate location if deemed applicable, by site staff, following consultation with the sponsor. At Visits 4, 6, and 8, study intervention will be administered as SC injections. Participants are required to fast for at least 8 hours prior to Visits 4, 6, and 8. Participants are permitted to drink water during this period of fasting until 1 hour before blood sampling. Blood and urine sampling must be performed prior to administration of study intervention. PK sampling to be performed at Visits 4, 6, and 8. On Visits 4, 6, and 8, PK and ADA sampling must be done pre-dose. An abbreviated physical examination is required at the visits as well as ECG and vital signs examination.

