#### 9.4.1 General Considerations

Unless otherwise stated, the safety analysis set will also be used for the presentation of all demographic and disposition data. If not otherwise specified, baseline refers to the last measurement prior to study intervention administration.

Statistical tests will be performed using two-sided test at a 5% significance level, if not explicitly stated otherwise. The SAS® version 9.3 or higher will be used for the data analysis.

A complete set of raw data listings will be appended to the final CSR. All tables, figures and listings will be presented in portable document format (PDF) without any manual editing, ie, they will appear unmodified as programmed by means of the statistical package.

All results will be presented by treatment with descriptive statistics appropriate to the nature of the variables. Demographic and baseline characteristics will be presented as follows; for continuous variables, the number of non-missing observations, mean, SD, SEM, 95% CI of the mean, median, first and third quartiles, minimum and maximum, will be presented; for categorical variables: counts (n) and percentages (%) (where specified) will be presented. These summaries will be provided by time point of assessment as appropriate.

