**Table 4 Analysis visit windows for unscheduled visits**

Analysis visit (AVISIT)	Visit Window (Days)
UNS 1	2 – 5
UNS 2	11 – 18
UNS 3	NA
UNS 4	33 – 38
UNS 5	48 – 52
UNS 6	62 – 66
UNS 7	76 – 79
UNS 8	88 – 91
UNS 9	>=177

The unscheduled visits will be numbered sequentially with an increment of 0.1. For example, if two measurements are done in the unscheduled visits that occur between visit Day 29 and Day 43, then these unscheduled visits will be numbered UNS 4.1 and UNS 4.2 in the order they occurred. The unscheduled visits are not summarized in tables but only presented in listing.

For the purpose of the statistical analysis:

- the baseline value used for statistical analyses is the last available value among those in the baseline analysis visit window. If several measurements are collected during the selected day, the average (for numeric values)/worst (for categorical values) of the measurements is taken. If there are several categorical values corresponding to the worst case, then the last measurement registered in eCRF will be taken.
- all the other post baseline visit values: If more than one measurement falls in the same visit window but in different days, the nearest to the scheduled visit day is taken. If several measurements are collected within the same distance from the scheduled study day, the data of the earlier visit after the scheduled study day within that window is used. If several measurements are collected during the selected day (selected timepoint within the day for PK), the average (for numeric values)/worst (for categorical values) of the measurements is taken. If there are several categorical values corresponding to the worst case, then the last measurement registered in eCRF will be taken. For coagulation parameters and complement activation panel if the selected day is a dosing day (except Day 1), two timepoints within the day need to be considered (pre-dose and 2h post-dose).

Averages are calculated after LLOQ replacement as reported in the following sections.

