### 4.1.1 MMRM assuming a log-normal distribution

An MMRM will be fitted on log-transformed change from baseline. Log-transformed change from baseline is calculated as the visit value in natural logarithm minus the baseline value in natural logarithm.

The visit statistically tested within the MMRM model is week 12 (day 85). All previous available data on scheduled visits will be used in the model. Fixed factors of the model will be treatment, visit and treatment\*visit interaction. The natural log-transformed baseline value of the outcome variable will be used as a covariate. Visits within subjects will be considered as repeated measurements.

Comparisons derived from the model will be:

- AZD8233 **CCI** versus placebo,
- AZD8233 **CCI** versus placebo
- AZD8233 **CCI** versus placebo
- AZD8233 **CCI** versus AZD8233 **CCI**
- AZD8233 **CCI** versus AZD8233 **CCI**
- AZD8233 **CCI** versus AZD8233 **CCI**

The REML approach will be used for the estimation of the variance and covariance parameters of the linear mixed model; two-sided difference test, with alpha level at 5% will be used for the comparisons and for the t-type confidence interval calculation.

The model will be fitted with an unstructured covariance structure and the Kenward-Roger correction applied to obtain the degrees of freedom.

In case the model will not converge for any reason, the following hierarchical model fitting procedure will be adopted:

1. The MMRM will be fitted using a SP(POW) covariance structure; Visit will be expressed as scheduled visit days to accomplish the variance-covariance matrix estimation.
2. The MMRM will be fitted using a CS covariance structure
3. An ANCOVA model will be used

The reportable results from the model will be:

- The LSmean and their 95% CI for each group for the log-transformed change from baseline
- Back transformed LSmean for each group, which correspond to the estimated relative change from baseline; back transformed LSmean is derived as  $[\text{EXP}(\text{LSmean})]$ .
- 95% CI of the back transformed LSmean for each group; 95% CI of the back transformed LSmeans is derived as  $[\text{EXP}(\text{lower limit of the 95\% CI of the LSmean})]$ ;  $[\text{EXP}(\text{upper limit of the 95\% CI of the LSmean})]$ .
- The geometric mean ratio between active groups and the control group; the ratio is calculated as  $\text{EXP}(\text{of the LSmean of the difference})$

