#### 4.1.2 MMRM assuming a normal distribution

An MMRM will be fitted on percent change from baseline. Percent change from baseline is calculated as the visit value minus the baseline value divided by the baseline value \*100.

The visit statistically tested within the MMRM is week 12 (day 85). All previous available data on scheduled visits will be used in the model. Fixed factors of the model will be treatment, visit and treatment\*visit interaction. The baseline value of the outcome variable will be used as a covariate. Visits within subjects will be considered as repeated measurements.

Comparisons derived from the model will be:

- AZD8233 **CCI** versus placebo,
- AZD8233 **CCI** versus placebo
- AZD8233 **CCI** versus placebo
- AZD8233 **CCI** versus AZD8233 **CCI**
- AZD8233 **CCI** versus AZD8233 **CCI**
- AZD8233 **CCI** versus AZD8233 **CCI**

The REML approach will be used for the estimation of the variance and covariance parameters of the linear mixed model; two-sided difference test, with alpha level at 5% will be used for the comparisons and for the t-type confidence interval calculation.

The model will be fitted with an unstructured covariance structure and the Kenward-Roger correction applied to obtain the degrees of freedom.

In case the model will not converge for any reason, the following hierarchical model fitting procedure will be adopted:

1. The MMRM will be fitted using a SP(POW) covariance structure; Visit will be expressed as scheduled visit days to accomplish the variance-covariance matrix estimation.
2. The MMRM will be fitted using a CS covariance structure.
3. An ANCOVA model will be used.

The reportable results from the model will be:

- The LSmean and their 95% CI for each group for the percent change from baseline
- The LSmean of the difference between active groups and the control group
- The 95% CI of the LSmean of the difference
- P-value of the LSmean of the difference

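### Should the LDL-C, PCSK9 and triglyceride models also adjust for the pre-dose value taken at Visit 2?

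*SAP*

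**What the plan says.** Protocol 8 (General description of visits) states: "Visit 2 (Day -7 to Day -1) will include an blood sample collection for LDL-C, PCSK9, and triglycerides". The Schedule of Activities has the same three analytes again at Visit 3. Both samples are fasting: "Participants are required to fast for at least 8 hours overnight prior to all study visits except for Visit 1". Footnote h covers timing on Day 1: "Samples to be obtained pre-dose on dosing days".

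Both values fall in the baseline window of SAP Table 3. Of these, "the baseline value used for statistical analyses is the last available value among those in the baseline analysis visit window", and averaging applies only within the selected day, so Visit 2 and Day 1 are never combined. Protocol 9.4.1 agrees: "baseline refers to the last measurement prior to study intervention administration".

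Each model carries one baseline term. For log-scale LDL-C and PCSK9 (SAP 4.1.1): "The natural log-transformed baseline value of the outcome variable will be used as a covariate". For percent change in LDL-C and the other lipids, triglycerides included (SAP 4.1.2): "The baseline value of the outcome variable will be used as a covariate".

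Visit 2 still has two uses. Its LDL-C and triglyceride values decide eligibility (Protocol 5.1). It also becomes the baseline if the Day 1 sample is missing or cannot be placed before the first dose (SAP Table 3, footnote a).

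**The concern.** A second fasting, pre-randomisation measurement of the outcome is already scheduled for every participant, and no efficacy model uses it when Day 1 is available. A single lipid value carries biological and assay noise, so two values could predict Week 12 better than one. Adjusting for both would not bias the comparison of arms and would need no extra sample. What would be at stake is the width of the intervals. That matters most for mid versus high dose, where Protocol 4.3 aims to show that raising the dose above the mid dose brings no clinically significant further LDL-C reduction.

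**Working it through.** **1. The plan's own figure.** Inputs from Protocol 9.2: difference 0.33, SD 0.3, two-sided 5% t-test, 20 per arm, 90% power. Noncentrality = 0.33 / (0.3 × √(2/20)) = 0.33 / 0.0949 = 3.48 on 38 df, so power is 92.4%. The smallest n reaching 90% is 19. At 27 per arm (108/4), noncentrality = 0.33 / 0.0816 = 4.04 and power is 97.8%. The stated 90% is met with the single baseline, even if 0.3 is already the residual SD.

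**2. What a second baseline can add.** Let a be the correlation of Day 1 with Week 12, b that of Visit 2 with Week 12, and r that between the two pre-dose values. The documents give none of these, so all are assumed. At a single visit:

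- residual variance with Day 1 only: 1 − a²
- with both: 1 − (a² + b² − 2abr)/(1 − r²)

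The gain is zero when b = a × r, that is, when Visit 2 relates to Week 12 only through Day 1.

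| a | b | r | Variance ratio, both vs Day 1 only |
|---|---|---|---|
| 0.5 | 0.5 | 0.7 / 0.8 / 0.9 | 0.941 / 0.963 / 0.982 |
| 0.5 | 0.45 | 0.7 / 0.8 / 0.9 | 0.974 / 0.991 / 1.000 |
| 0.7 | 0.7 | 0.7 / 0.8 / 0.9 | 0.830 / 0.893 / 0.949 |

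Worked example (0.5, 0.45, 0.8): (0.25 + 0.2025 − 0.36)/0.36 = 0.257, and (1 − 0.257)/0.75 = 0.991.

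Estimating the extra slope costs about 1% at 27 per arm (1.5% at 20), and the table does not include this. A shortfall of 0.05 in Visit 2's correlation therefore removes the net gain at r of 0.8 or more.

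**3. The planned repeated-measures model.** Simulating SAP 4.1.1 (seven visits, unstructured covariance, 27 per arm, complete data) gives these Week 12 variance ratios:

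- Equal prediction, q = 0.5, r = 0.8 (q being the correlation of each pre-dose value with the post-dose visits): a saving of about 1 to 3%.
- Visit 2 adds nothing beyond Day 1: 1.004 to 1.011.
- q falling from 0.7 at Week 1 to 0.3 at Week 12, one Visit 2 slope shared across visits: 1.01 to 1.04, a loss.
- Same decline, Visit 2 slope free by visit: 0.89 to 0.90. Freeing the Day 1 slope by visit and leaving Visit 2 out gives 0.88 to 0.89, so the gain comes from the free slope and not from the second sample.
- Mid versus high dose, with placebo q = 0.7 and active q = 0.2 to 0.3: 0.98 to 1.01.

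**4. What this does to an interval.** With residual SD 0.3, 27 per arm and t = 1.983 (104 df), the half-width is 1.983 × 0.3 × √(2/27) = 0.1619. Around a geometric mean ratio of 1, the 95% interval is 0.850 to 1.176. With 3% less variance it is 0.853 to 1.173, and with 5% less, 0.854 to 1.171.

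**5. The cost elsewhere.** Sensitivity analysis 2 (SAP 4.1.4) imputes some values from placebo alone. Assume its Week 12 regression uses baseline and six earlier visits (p = 7). The prediction-variance factor is (n+1)(n−2)/(n(n−p−2)). Adding Visit 2 (p = 8) moves it from 1.440 to 1.525 at n = 27 (6% more) and from 1.718 to 1.890 at n = 20 (10% more) if Visit 2 adds nothing. That exceeds the 3 to 5% saving illustrated in step 4.

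**The case for a change.** The best case for adding Visit 2 is that the sample is already taken, the covariate is legitimate, the endpoint definition would not change, and with a visit-specific slope the simulated loss is at most about 1.5%. If both pre-dose values correlate 0.7 with Week 12 and 0.7 with each other, the variance falls by 17%. If 0.3 is the residual SD after one baseline, power at 20 per arm would then rise from 92.4% to 96.0%.

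The facts and the validity of the adjustment stand. The size does not. The favourable case needs two fasting samples about a week apart or less, on stable medication (Protocol 5.1), to agree no better than Day 1 agrees with a Week 12 value under a drug expected to lower LDL-C strongly (Protocol 2.3.2 and 4.3). The 1.5% limit comes from complete data on the log scale. Missing data and the percent-change model were not simulated, although 108 are randomised to secure 80 completers.

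The change would also touch several parts of the plan: SAP 4.1.1 and 4.1.2, a rule for missing Visit 2 values (and for rescreened participants, who may have more than one), both sensitivity analyses, and SAP Section 6. Triglycerides would have a different model from the other lipids. SAP 1.1 rests its type I error argument partly on the efficacy model staying fixed at the primary analysis, and the documents do not show whether a change could still be made before unblinding.

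**Conclusion.** The concern does not hold. Protocol and SAP give the same baseline rule, the models adjust for that baseline, and leaving out a second pre-randomisation value creates no bias, contradiction or gap. The stated power is met without it. Any gain is in precision only: over the assumed correlations the Week 12 variance ratio runs from 0.83 to 1.04, and in the central equal-prediction case (q = 0.5, r = 0.8) the simulated saving is about 1 to 3%. It disappears if Visit 2 predicts slightly less well than Day 1, and it is nil or close to nil for mid versus high dose if strong lowering weakens the baseline correlation. These sizes rest on correlations that the documents do not give. Reasonable statisticians could choose either model, and no change to the plan is needed.

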### 3.1.3 Study phase windows

For the purpose of the statistical analysis adverse events, immunogenicity data, LDL-C, PCSK9, other lipid parameters, lipoprotein profile, laboratory evaluations, vital sign and ECG are allocated to the study phase in which they are collected as reported below. The allocation to the study phases is performed after the imputation of date of first and last doses of IP as in section 3.1.1. The allocation of the AEs to the study phases is performed after the imputation of AE start and AE end dates as reported in section 3.1.1.

**Table 5 Study phases**

Study phase	Phase Window for Analysis (Days)
Pre-treatment	before first dose of study IP (day <1 a )
On-treatment	> day 1 b to the end of study date

a Includes all measurements collected before first dose of IP. If the measurement is collected on day 1 it cannot be determined if it was done before or after the first dose of IP (due to missing time and/or planned time point), then it will be considered as collected after first dose of IP.

b Includes all measurements collected on the day of first dose of IP, at the time of IP intake and after.

## 3.2 Baseline assessments and other subject-specific characteristics

Demographic and subject characteristics, medical history and nicotine and alcohol use are collected pre-treatment as per section 1.2.

### 3.2.1 Demographic and subject characteristics

Demographic and subject characteristics include age, age group (<50; >=50 -<65; >=65), sex, race, ethnic group, country, region, height (cm), weight (kg), body mass index (BMI) (kg/m^2). Age is the age at screening as reported in the eCRF, BMI (kg/m^2) is calculated as: weight (kg) / [(height (cm)/100)].

Height, weight and BMI are allocated to the concerning analysis visits as per section 3.1.2. Evaluations with missing or partially missing dates cannot be imputed to any analysis visit. Only baseline values are included in the demographic and subject characteristics.

